3.3. Number of Subjects

Considering the 2016 tumor registry-reported analytic case volume at each study site for thoracic, GI and Gyn cancers, 12 patients per month per site for each of surgical and medical oncology is a highly conservative estimate of accrual. With 6 sites, assuming equal cluster size, 432 patients will be enrolled both for each period and for each cohort. Thus, a minimum of 6048 patients are expected to be enrolled to the SW-CRT. (Table 3) We will not have a cap for the number of participants for each site. Thus, the number of participants at the end of the study will be different from site to site.

Table 3: Conservative estimates of the accrual numbers for the SW-CRT

Site	MO/ Surg	Period 1 (Run-in)	Period 2	Period 3	Period 4	Period 5	Period 6	Period 7	Total
BAPT	MO	72	72	72	72	72	72	72	504
	Surg	72	72	72	72	72	72	72	504
MMC	MO	72	72	72	72	72	72	72	504
	Surg	72	72	72	72	72	72	72	504
DFCI	MO	72	72	72	72	72	72	72	504
	Surg	72	72	72	72	72	72	72	504
LCI	MO	72	72	72	72	72	72	72	504
	Surg	72	72	72	72	72	72	72	504
DHMC	MO	72	72	72	72	72	72	72	504
	Surg	72	72	72	72	72	72	72	504
WVU	MO	72	72	72	72	72	72	72	504
	Surg	72	72	72	72	72	72	72	504
Total	MO	432	432	432	432	432	432	432	6048
	Surg	432	432	432	432	432	432	432	

Notes:

- The length of each period is 6 months. The run-in period will be at least 6 months, and it will be adjusted so that the total number of eligible episodes under the control condition can be identical to that under the intervention condition.
- The cells colored by blue or grey indicate the periods where the intervention is rolled out in that hospital.

A subset of eSyM+ patients will be asked to complete a research questionnaire called the “SASS Questionnaire (eSyM+ version)” asking about their Self-efficacy, Attainment of information needs, Symptom burden, and Satisfaction with care.

Table 4: SASS Questionnaire accrual numbers (Survey Cohort)							
Site	Surgery			Medical Oncology			Totals
	eSyM- Version	eSyM+ Version	eSyM+ Non-Responder Version	eSyM- Version	eSyM+ Version	eSyM+ Non-Responder Version	
Site 1	75	75	15	75	75	15	330
Site 2	75	75	15	75	75	15	330
Site 3	75	75	15	75	75	15	330
Site 4	75	75	15	75	75	15	330
Site 5	75	75	15	75	75	15	330
Site 6	75	75	15	75	75	15	330
Totals	450	450	90	450	450	90	1,980

eSyM+ : Intervention condition
eSyM- : Control condition

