6.2. Data Analysis

Analysis of Outcomes classified as Type 1:

- For descriptive purposes, we will estimate crude means for continuous outcomes and crude proportions for dichotomous outcomes and calculate corresponding 95% confidence intervals by site. The coefficient of variation is calculated using the site-specific point estimates.
- Next, we estimate the overall mean (or proportion). To this end, a weighted mean and corresponding 95% confidence interval will be calculated using the site-specific point estimates and their standard error estimates, using the inverse of the site-specific variance estimates for the weights.
- In addition, generalized linear models (GLMs) will be used to investigate factors associated with the outcome. In the GLMs, we will account for site variability by treating "site" as a fixed effect. For modeling continuous outcomes, we will use the identity link function. For dichotomous outcomes, the logit link function is used.

Analysis of Outcomes classified as Type 2:

- We will calculate the site-period-specific means (or proportions), adjusted for the factors potentially associated with the outcome. We will calculate the coefficient of variations across sites and also across periods, respectively.
- To this end, we will use generalized linear mixed-effects models (GLMMs). In GLMMs, we will account for site variability by treating "site" as a fixed-effect, secular trend by treating "period" as a fixed-effect, and within-subject variability by treating "subject" as random-effects. For modeling continuous outcomes, we will employ the identity link function. For

dichotomous outcomes, the logit link function will be utilized. G-computation will be used to derive the site-period-specific means (or proportions).

- We will also calculate the site-specific, period-specific, and overall means (or proportions) and corresponding 0.95 confidence interval by taking a weighted average of the site-period-specific mean values (or proportions) obtained through GLMMs. The reciprocal of the variance-covariance matrices of the site-period-specific mean values (or proportions) will be used as the weight.

Analysis of Outcomes classified as Type 3:

- For descriptive purposes, we will estimate crude means for continuous outcomes and proportions for dichotomous outcomes and calculate corresponding 95% confidence intervals by intervention group (eSyM+ vs. eSyM-) and site.

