8.1. Outcomes and summary measures

The outcomes investigated in Aim 3a in the SIMPRO study are classified into four groups, depending on the data source and data collection schedule. **Table 13** shows the details of the groups and the disposition of each outcome in Aim 3a.

Table 13: Outcomes in Aim 3a

Type	Outcome Type in the SIMPRO study	Example outcomes in Aim 3a
1	Measured at one single time point only either in post-intervention (the intervention condition) or in pre-intervention (the control condition) for all or selected subjects (patients or providers)	Qualitative feedback Pt satisfaction with eSyM tool System Usability Items FIM item AIM items (acceptability) NOMAD items CSAT items # of med onc clinics continuing to use eSyM after stepped wedge period # of surg clinics continuing to use eSyM after stepped wedge period # of clinics that have >= 1 team conducting eSyM severe symptom outreach (e.g. using IB alerts) # of clinics that have >= 1 team conducting eSyM population symptom mgmt (e.g. using reports) Clicker questions (readiness + appropriateness for intervention) [pre-intervention only]
2	Measured at multiple time points (periodically) only in post-intervention period for all or selected subjects (patients or providers)	% of patients eligible to use eSyM completing 1+ qnr (PRIMARY IMPLEMENTATION OUTCOME) # pts assigned to eSyM/total # of pts with index condition on eSyM registry # reporting eSyM once, 25%, 50%, 75% of prompts Clinical staff responses to eSyM reports (InBasket + Telephone Encounters + Messages) Patient eSyM Total Usage Rate (w/MyChart) - up to 1 year after go-live Patient eSyM Total Usage Rate (w/ or w/o MyChart) - up to 1 year after go-live Patient eSyM Weekly Usage Rate (w/MyChart) - up to 1 year after go-live Patient eSyM Weekly Usage Rate (w/ or w/o MyChart) - up to 1 year after go-live % of MyChart Patients w/ documented outreach - up to 1 year after go-live % of patients with eSyM assigned w/ documented outreach - up to 1 year after go-live % of weekly patients responding to eSyM w/ documented outreach - up to 1 year after go-live % of weekly responders reporting moderate-severe symptoms - up to 1 year after go-live % of weekly responders reporting severe symptoms - up to 1 year after go-live

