8.2. Data Analysis

Analysis of Outcomes classified as Type 1: See Section 6.2

Analysis of Outcomes classified as Type 2: See Section 6.2

Analysis of Outcomes classified as Type 3: See Section 6.2

Analysis of Outcomes classified as Type 4: See Section 6.2

9. Analysis for Aim 3b: The sustainability of ePRO symptom management within a health system

Hypotheses:

- (1) We hypothesize that 3 or more of our health systems will continue eSyM reporting for MO patients beyond 90 days.
- (2) We hypothesize that tapering the dedicated nursing support provided by the study does not affect the effect of eSyM on clinical/utilization outcomes.

Analysis:

We will evaluate sustainability at the patient, clinic and health system level using simple rates and proportions. To evaluate sustainability, we will examine the consequences of withdrawing grant-funded nursing support for symptom management in the post-implementation period. We will compare outcomes from Period 6 (study month 45-50, all sites eSyM+) and the post-Implementation (Post-I; study months 51-56). Sites are trained and empowered to manage eSyM autonomously without research study staff. Then, during post-implementation, dedicated nursing support to monitor eSyM is *tapered* in half the sites (see Figure C2). To examine whether backing off on the study support attenuates the effect, we will perform difference in difference analysis. For each outcome, we will calculate the difference between Post-I and Period 6 outcomes by site. We then calculate the difference between site groups and the corresponding 95% confidence intervals.

10. Analysis for Aim 3c (Penetration and scalability of ePROs for symptom management) and Aim 3d (Extent of adaptation of ePRO systems over the course of the implementation process)

A mixed-methods approach:

Our analytic approach will integrate qualitative and quantitative data to obtain an informative description of factors that influence implementation at the level of 1) the practice site, 2) the health system, and 3) the entire project. The CFIR schema will facilitate comparisons, across settings and timepoints. First, we will analyze the qualitative and quantitative data separately. Next, we will use a weaving approach to integrate each source narrative to report findings on a theme-by-theme basis.²⁴

Qualitative:

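### Inverse-variance pooling of proportions in SAP Section 6.2 over-weights sites near 0% or 100%, so the overall adoption figure is not the share of eligible patients who used eSyM

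*SAP*

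**What the plan says.** SAP Section 6.2 has two pooling rules that matter here.

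- **Type 1** (one time point, one condition). The inputs are "crude proportions for dichotomous outcomes and calculate corresponding 95% confidence intervals by site". The overall value is a weighted mean, "using the inverse of the site-specific variance estimates for the weights".
- **Type 2** (repeated, post-intervention only). A logit mixed model has site and period as fixed effects and subject as random. Then "G-computation will be used to derive the site-period-specific means (or proportions". Site-specific, period-specific and overall values are weighted averages of these: "The reciprocal of the variance-covariance matrices of the site-period-specific mean values (or proportions) will be used as the weight".

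Table 13 (Section 8.1) lists under Type 2 the percentage "of patients eligible to use eSyM completing 1+ qnr (PRIMARY IMPLEMENTATION OUTCOME", and Section 8.2 sends it to this rule: "Analysis of Outcomes classified as Type 2: See Section 6.2". Under Type 1, the same table lists clinic-level items such as the number "of med onc clinics continuing to use eSyM after stepped wedge period".

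Section 6.2 gives no size-based or equal weights, no transformed scale for pooling, no between-site variance term, no standard-error method for a crude proportion and no rule for a site at 0% or 100%. It does plan a coefficient of variation across sites, so it allows for sites to differ.

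**The concern.** Inverse-variance weighting suits several estimates of one common quantity whose variances do not depend on that quantity. Neither condition holds here. Sites may adopt at different rates, and a proportion's variance is a function of the proportion. The result is a weighted average whose weights depend on the outcome. It equals the share of eligible patients only when site rates agree or happen to balance around 50%.

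At stake is the headline adoption rate of a hybrid effectiveness-implementation trial. A reader will take it as the proportion of eligible patients who completed at least one questionnaire. The primary effectiveness outcome (EDTR at Day 30) is analysed under Section 4.4 and is not affected.

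**Working it through.** The documents state no pooled proportion, adoption target or precision, so there is no plan figure to reproduce.

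**Inputs from the SAP.** Section 3.3 sets accrual: "12 patients per month per site for each of surgical and medical oncology is a highly conservative estimate of accrual". That is 12 × 6 = 72 per period and cohort, and 72 × 7 × 2 = 1008 per site; six sites give 6048, as stated. Section 3.1 intends equal intervention and control numbers within each site, so 1008 / 2 = 504 eSyM+ patients per site. Site adoption rates are **not given**; those below are assumptions.

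**Type 1.** Var(p) = p(1−p)/n, weight w = n/[p(1−p)], pooled value = Σwp / Σw. With equal n this is Σ[1/(1−p)] / Σ[1/(p(1−p))].

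Sites at 10, 20, 30, 40, 50, 60%:
- Σ 1/[p(1−p)] = 11.111 + 6.250 + 4.762 + 4.167 + 4.000 + 4.167 = 34.456
- Σ 1/(1−p) = 1.111 + 1.250 + 1.429 + 1.667 + 2.000 + 2.500 = 9.956
- Pooled = 9.956 / 34.456 = 28.9%, against a patient-weighted 35.0%
- SE = 1/√(504 × 34.456) = 0.0076, so the 95% CI is 27.4 to 30.4%, which excludes 35.0%
- The 10% site holds 11.111 / 34.456 = 32% of the weight

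**Type 2.** I fitted a logistic site + period model to the planned live site-period cells (one record per patient, no random effect, no true period effect), then applied G-computation and a delta-method covariance. Live cells: 6 + 5 + 4 + 4 + 5 + 6 = 30. The last two columns read the weight as the inverse of the diagonal, or as a pseudo-inverse of the full matrix.

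| Assumed site rates (six sites of 504) | Patient-weighted | Type 1 rule | Type 2, diagonal | Type 2, pseudo-inverse |
|---|---|---|---|---|
| 30, 35, 40, 45, 50, 55% | 42.5% | 42.0% | 41.8% | 42.0% |
| 20, 30, 40, 50, 60, 70% | 45.0% | 43.3% | 42.4% | 43.3% |
| 10, 20, 30, 40, 50, 60% | 35.0% | 28.9% | 25.8% | 28.9% |
| 5, 30, 40, 45, 50, 60% | 38.3% | 24.8% | 19.0% | 24.8% |

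In the last row the 5% site carries 21.053 / 42.188 = 50% of the Type 1 weight.

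**Singular matrix.** With site and period main effects only, all 30 cell proportions are functions of 6 + 6 − 1 = 11 coefficients. Their 30 × 30 covariance matrix has rank 11, so the reciprocal that the SAP specifies does not exist.

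**Equal true rates.** Sites that are low by chance also get a small estimated variance and so more weight. Simulating six sites with a true 10% and n = 75 each (the eSyM+ survey target per site and cohort in Table 4), the Type 1 estimate averages 9.0% and its nominal 95% CI covers about 81%. The 0.2% of runs with a site at zero cannot be computed and are left out.

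**Boundary.** With the usual standard error, a site at 0% or 100% has variance 0 and weight 1/0. The documents do not give the number of clinics per site. Assuming 6 clinics per site and 90% continuation, one site is at 100% with probability 0.9^6 = 0.531, and at least one of six with probability 1 − (1 − 0.531)^6 = 99%.

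**The case against.** The case for leaving the rule alone has several sound parts.

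- **Size still counts.** A reader might infer that extreme sites dominate whatever their number of patients. They do not, because n is in the weight. A 60% site outweighs a 10% site once it has more than 11.111 / 4.167 = 2.67 times the patients. Section 3.3 sets no cap and expects unequal sites, while the table above assumes equal ones.
- **The shift may be small.** It is 0.5 to 1.7 points in the milder patterns. Only a site well away from the rest and near a boundary gives 6 points or more.
- **An undefined headline is not supported.** A reader might infer that the primary implementation outcome cannot be computed. The model smooths a single site-period cell at 0%. Failure needs a whole site at 0% or 100%, which is very unlikely with about 504 patients unless adoption is near zero or complete.
- **The 15 non-responder surveys per site are not an example.** One can calculate a 75% chance of some site at 0/15 when the true rate is 10%. But no Type 1 entry in Table 12 or 13 is a proportion from that survey. The usability and satisfaction items are in the eSyM+ versions, with 75 per site and cohort; there the corresponding chance is 0.2%.
- **Site rates will be visible.** Site or site-period estimates are planned, and no test or target depends on the pooled value. Section 9 also evaluates clinic-level sustainability with simple proportions.

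These points limit the size and reach of the problem. They do not make the stated weights right. How far the result departs from the share of patients depends on site rates that nobody could know when the rule was written.

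**Conclusion.** The concern holds as a bias in a stated rule. For proportions, both weighting sentences in Section 6.2 give an overall value that differs from the patient-level share whenever site rates are unequal and do not balance around 50%. The shift runs from about half a point to 13.5 points under the Type 1 rule. Under Type 2 it is similar, or larger with diagonal weights. All of these sizes rest on assumed site rates and six equal sites; the Type 2 values also rest on a model without covariates or subject effects.

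Two narrower defects stand beside it. Type 1 items with few units per site cannot be pooled at 0% or 100% if the usual standard error is used (the SAP names none). The Type 2 covariance matrix cannot be inverted with site and period main effects only. This should be corrected because it concerns the primary implementation outcome, but it does not touch the effectiveness result.

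**What to change.** For proportions, replace the two weighting sentences in Section 6.2 with weighting by number of eligible patients (or units, for clinic-level items):

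- **Type 1:** the crude pooled proportion.
- **Type 2:** G-computation averaged over the actual eSyM+ patients.
- **Interval:** model-based (delta method), or a patient-level bootstrap within sites.
- **Beside it:** the equal-weight site mean and the site-specific rates.
- **Kept:** the SAP's inverse-variance estimate as a labelled sensitivity result, wherever it can be computed. The June 2024 addendum already reports observed episode frequencies and convergence problems, so the change comes after data were examined and should be recorded as such.

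No new data are needed. The costs are that the largest site gains influence, which the equal-weight mean makes visible, and that the interval describes these six sites only. An interval meant to generalise beyond them would not be reliable with six clusters.

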- Using these results, the difference between the intervention condition (eSyM+) and the control condition (eSyM-) along with a corresponding 95% confidence interval will be calculated for each site. In addition, using the point estimates from the six sites, we will calculate the coefficient of variation of the difference between conditions.
- We will then estimate the overall between-conditions difference integrating the site-specific differences. Specifically, a weighted average and corresponding 95% confidence interval will be calculated, using the site-specific point estimates their standard error estimates, where the reciprocal of the site-specific variance estimates will be used for the weights.
- In addition, generalized linear models (GLMs) will be used to investigate factors associated with the outcome. In the GLMs, we will include the intervention indicator, “site” and other factors (i.e., age (at cancer diagnosis for medical oncology patients and at index surgery for surgical patients), sex, employment status, education, ability to pay bills, and technology confidence) as independent variables. For modeling continuous outcomes, we will employ the identity link function. For dichotomous outcomes, the logit link function will be utilized. Note that, when more appropriate (where some subjects have data from both pre- and post-intervention periods), we will use GLMMs by treating “subject” as random-effects instead of GLMs for some outcomes.

Analysis of Outcomes classified as Type 4:

- We will estimate the intervention effect on each outcome.
- To this end, analyses similar to those for Aim 2a (see Section 4) will be conducted. GLMMs will be used with the identity link function for continuous outcomes and with the logit link function for dichotomous outcomes. The intervention effect will be summarized as the mean difference and odds ratio for continuous outcomes and dichotomous outcomes, respectively, and reported with a corresponding 95% confidence interval and p-value.

Interpretation of the PROMIS scores: Note that Yost and Cella have reported minimally important difference (MID) ranges for five PROMIS domains including fatigue, pain, depression, anxiety, and physical functioning^{17,18} Cella recommends using 0.5 SD as the MID for PROMIS scales^{19,20}

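### For PROMIS and CAHPS outcomes, the coefficient of variation of six site differences is unstable near zero and counts sampling error as site variation

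*SAP*

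**What the plan says.** SAP 6.2 sets out the Type 3 analysis in steps. The by-site step is descriptive: "For descriptive purposes, we will estimate crude means for continuous outcomes and proportions for dichotomous outcomes", by intervention group and site. From these the SAP forms the eSyM+ minus eSyM- difference, which "along with a corresponding 95% confidence interval will be calculated for each site". It continues, on the basis of the six site point estimates: "we will calculate the coefficient of variation of the difference between conditions". The six differences are then pooled as a weighted average, "where the reciprocal of the site-specific variance estimates will be used for the weights". A regression follows: "In the GLMs, we will include the intervention indicator, “site” and other factors", these being patient characteristics.

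Section 7.2 sends the CAHPS outcomes through the same steps. The site standard errors enter the pooled estimate but not the CV. For Type 3 outcomes no Q test, I², tau or intervention-by-site term is specified. The region subgroup in SAP 4.5 is written for the EDTR rate. The June 2024 addendum does not change section 6.2.

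CVs are also planned for Type 1 outcomes ("The coefficient of variation is calculated using the site-specific point estimates") and Type 2 outcomes ("We will calculate the coefficient of variations across sites and also across periods, respectively"), but there they describe means or proportions.

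**The concern.** A CV is a standard deviation divided by a mean. It is interpretable for a quantity that is positive and well away from zero. A between-condition difference is signed, and it is zero under the null hypothesis. As the mean difference approaches zero the CV grows without limit, and it changes sign when the mean does. The same spread between sites therefore gives a different CV at each size of average effect.

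Separately, six site estimates differ by chance even when the true effect is identical everywhere. A CV of point estimates has no term that removes this.

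At stake is the only single-number summary of between-site variation in the eSyM effect that the SAP plans for PROMIS and CAHPS. A large value could be read as eSyM working at some sites and not at others when the figure reflects only a small average effect and modest samples.

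**Working it through.** The SAP gives no expected CV, heterogeneity target or power for Type 3 outcomes, so there is no planned figure to reproduce.

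**Inputs from the documents**
- SAP Table 4: per site and per cohort (Surgery, MO), 75 eSyM-, 75 eSyM+ and 15 eSyM+ Non-Responder surveys. Check: 6 × 2 × (75 + 75 + 15) = 1,980, the stated total.
- SAP 6.2: 0.5 SD is cited as the minimally important difference for PROMIS.

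**Assumptions, not in the documents**
- CV = sample SD of the six differences / mean (absolute mean in the table below); outcome SD scaled to 1; normal site estimates.
- True effects of 0 to 0.5 SD; true between-site SD (tau) of 0 or 0.1 SD.
- Two ways of forming the groups, because 6.2 does not say which applies. One is 75 v 75 per site and cohort. The other is 180 v 150 per site, with cohorts pooled and Non-Responders counted as eSyM+: 2 × (75 + 15) = 180 and 2 × 75 = 150.

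**Standard error of one site's difference**
- 75 v 75: √(1/75 + 1/75) = 0.163 SD
- 180 v 150: √(1/180 + 1/150) = 0.111 SD

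**Absolute CV when true site variation is zero** (400,000 simulated sets of six sites; median, with 2.5th to 97.5th percentile)

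| Common true effect | 180 v 150 | 75 v 75 |
|---|---|---|
| 0.1 SD | 1.05 (0.37 to 7.0) | 1.54 (0.46 to 24) |
| 0.2 SD | 0.52 (0.21 to 1.13) | 0.77 (0.29 to 2.45) |
| 0.5 SD | 0.21 (0.09 to 0.37) | 0.31 (0.13 to 0.57) |

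The true CV is 0 in every cell. As a hand check, the median sample SD of six values is about 0.933 × SE. For 75 v 75 that is 0.152, and 0.152/0.5 = 0.30.

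**No true effect.** Here the CV equals √6 divided by a t variable with 5 degrees of freedom. By symmetry it is negative half the time. It exceeds 1 in absolute value when |t| < √6 = 2.449, which has probability 0.942. Its median absolute value is 2.449/0.727 = 3.37. None of these results involves the standard error or tau, so at zero effect the CV carries no information about site variation.

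**Response to real variation.** At an effect of 0.2 SD and tau = 0.1 SD (true CV 0.5), the median moves from 0.77 to 0.90 with 75 v 75, and from 0.52 to 0.70 with 180 v 150. The ranges overlap heavily.

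**Fixed spread, shifted mean.** Six differences with SD 0.121 give a CV of 0.24, 0.60, 1.21 and 6.04 at means of 0.5, 0.2, 0.1 and 0.02. It is undefined at 0 and -6.04 at -0.02. Cochran Q (75 v 75) is 5 × 0.121²/0.163² ≈ 2.74 throughout.

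**Behaviour of the alternative.** With tau = 0, Q rejects in 5% of studies whatever the mean effect. With tau = 0.1 SD, Q is distributed as (1 + tau²/SE²) times a chi-square on 5 degrees of freedom. The multiplier is 1.375 for 75 v 75 and 1.82 for 180 v 150. Q then rejects at the 5% level in 15% and 30% of studies. The moment estimate of tau is exactly zero (Q below 5) in 40% and 26%.

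**Types 1 and 2.** For a proportion of 0.5, sampling error alone gives a CV of √(0.25/150)/0.5 = 8% at n = 150. At n = 504, half of the 1,008 per-site minimum in SAP Table 3, it gives √(0.25/504)/0.5 = 4.5%.

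**The case against.** The strongest reply is that little depends on this statistic. It drives no test, estimate, power figure or decision. It builds on by-site results labelled descriptive, and a 95% interval is reported for each site, so a careful reader can see the sampling error. All of that stands, and it limits the weight of the point. It does not make the CV itself interpretable.

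A reader might infer that homogeneous sites would simply be presented as highly variable. The documents do not support that: the CV would appear beside six site intervals, which would overlap widely in that case. A reader might also infer that the effectiveness result is compromised, or that site heterogeneity in PROMIS and CAHPS is a principal product of the trial. Neither is supported. The pooled difference uses inverse-variance weights and does not involve the CV, and no document sets a heterogeneity objective or threshold for these outcomes.

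Extending the full criticism to Types 1 and 2 is also tempting. Means and proportions do not have this near-zero fault, and Type 2 values are model-adjusted. The 8% figure fits survey-sized samples only; several of these outcomes come from EHR or eSyM data on many more patients.

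Finally, SAP 4.4 itself says that six sites are too few for conventional random site effects, and tau rests on the same six sites. That is a fair caution about the remedy.

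**Conclusion.** The point holds for Type 3 outcomes. As specified, the CV is undefined or unstable when the mean difference is near zero, and at any effect size it includes sampling error. With no true site variation, the median absolute CV is about 1.0 to 1.5 at 0.1 SD, 0.5 to 0.8 at 0.2 SD and 0.2 to 0.3 at 0.5 SD. The lower figures rest on the 180 v 150 grouping and the higher on 75 v 75; both groupings and the effect sizes are assumptions. At 0.5 SD, the only effect size that section 6.2 cites, the CV can be computed but is still inflated rather than meaningless. The result at zero effect needs neither a sample size nor an outcome SD, only equal precision across sites.

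This is a fault in one descriptive summary, worth correcting because following the SAP would put a misleading figure in the report. For Types 1 and 2 the inflation is smaller and a change is optional.

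**What to change.** In SAP 6.2, for Type 3 outcomes (and so for CAHPS through 7.2), replace the CV of the differences with the between-site SD, tau, of the six site differences. Estimate it by REML on the outcome scale and report it with a 95% confidence interval and Cochran Q, beside the site-specific intervals already planned. State whether MO and Surgery are pooled and whether Non-Responders count as eSyM+ in the site differences.

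Add a sentence that, with six sites, a tau estimate of zero or a non-significant Q is not evidence of homogeneity. Its basis is the low power shown above: about 15% to 30% at tau = 0.1 SD.

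The cost is a wording change and standard software; the site estimates and standard errors are already produced. The price is in interpretation: the interval for tau will be wide, and real variation will often be estimated as none. If the Type 1 and Type 2 CVs are kept, a note that they include sampling error is enough.
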